11.44 Overall Objective Status

The overall objective status for an evaluation is determined by combining the patient's status on target lesions, target lymph nodes, non-target lesions, non-target lymph nodes, and new disease as defined in the following tables:

For Patients with Measurable Disease

Target Lesions & Target Lymph Nodes	Non-Target Lesions & Non-Target Lymph Nodes	New Sites of Disease	Overall Objective Status
CR	CR	No	CR
CR	Non-CR/Non-PD	No	PR
PR	CR Non-CR/Non-PD	No	PR
CR/PR	Not All Evaluated*	No	PR**
SD	CR Non-CR/Non-PD Not All Evaluated*	No	SD
Not all Evaluated	CR Non-CR/Non-PD Not All Evaluated*	No	Not Evaluated (NE)
PD	Unequivocal PD CR Non-CR/Non-PD Not All Evaluated*	Yes or No	PD
CR/PR/SD/PD/Not all Evaluated	Unequivocal PD	Yes or No	PD
CR/PR/SD/PD/Not all Evaluated	CR Non-CR/Non-PD Not All Evaluated*	Yes	PD

*See Section 11.431

** NOTE: This study uses the protocol RECIST v1.1 template dated 2/16/2011. For data collection and analysis purposes the objective status changed from SD to PR in the ACCRU protocol RECIST v1.1 template as of 2/16/2011 and to match RECIST v1.1 requirements.

12.0 Descriptive Factors

- Nephrectomy (Yes vs. No)

13.0 Treatment/Follow-up Decision at Evaluation of Patient

13.1 Patients who are CR, PR, or SD will continue treatment per protocol up to a maximum of 10 cycles or until PD whichever is first. After 10 cycles of treatment, treatment may be continued off study per physician discretion. Patients who are CR, PR, or SD after 10 cycles will move to Observation Phase of the trial (see section 13.2).

13.2 Observation:

Patients who complete protocol treatment, or discontinue protocol treatment due to unacceptable toxicity or other complicating disease, will be followed every 8 weeks (+/- 7 days) for a maximum of 2 years from the registration in the Observation Phase per Section 4.0 of the protocol.

13.3 Event Monitoring:

Patients who develop PD, choose alternative therapy, refuse treatment or refuse to be followed in observation at any time will go to the Event Monitoring phase and be followed every 6 months (+/- 30 days) for a maximum of 3 years from registration per Section 18.0 of the protocol. Treatment options for these patients are at the discretion of the treating physician.

13.4 Patients who develop PD in the CNS only should receive whole brain radiotherapy (WBRT) and continue treatment on study after completion of WBRT.

13.5 A patient is deemed *ineligible* if after registration, it is determined that at the time of registration, the patient did not satisfy each and every eligibility criteria for study entry. The patient may continue treatment off-protocol at the discretion of the physician as long as there are no safety concerns, and the patient was properly registered. The patient will go directly to the event-monitoring phase of the study (or off study, if applicable).

- If the patient received treatment, all data up until the point of confirmation of ineligibility must be submitted. Event monitoring will be required per Section 18.0 of the protocol.
- If the patient never received treatment, on-study material must be submitted. On-study material and the Off Treatment Form must be submitted. No further data submission is necessary.

13.6 A patient is deemed a *major violation*, if protocol requirements regarding treatment in cycle 1 of the initial therapy are severely violated that evaluability for primary end point is questionable. All data up until the point of confirmation of a major violation must be submitted. The patient will go directly to the event-monitoring phase of the study. The patient may continue treatment off-protocol at the discretion of the physician as long as there are no safety concerns, and the patient was properly registered. Event monitoring will be required per Section 18.0 of the protocol.

13.7 A patient is deemed a *cancel* if he/she is removed from the study for any reason before any study treatment is given. On-study material and the Off Treatment Form must be submitted. No further data submission is necessary.

14.0 Body Fluid Biospecimens: None**15.0 Drug Information**

The study drug is IND exempt because:

- The drug product is lawfully marketed in the United States.
- The investigation is not intended to be reported to FDA as a well-controlled study in support of a new indication and there is no intent to use it to support any other significant change in the labeling of the drug.
- In the case of a prescription drug, the investigation is not intended to support a significant change in the advertising for the drug.
- The investigation does not involve a route of administration, dose, patient population, or other factor that significantly increases the risk (or decreases the acceptability of the risk) associated with the use of the drug product (21 CFR 312.2(b)(1)(iii)).
- The investigation is conducted in compliance with the requirements of §312.7 (i.e., the investigation is not intended to promote or commercialize the drug product).

15.1 Pazopanib (Votrient®)

- 15.11 **Background:** Tyrosine kinase (multikinase) inhibitor; limits tumor growth via inhibition of angiogenesis by inhibiting cell surface vascular endothelial growth factor receptors (VEGFR-1, VEGFR-2, VEGFR-3), platelet-derived growth factor receptors (PDGFR-alpha and -beta), fibroblast growth factor receptor (FGFR-1 and -3), cytokine receptor (cKIT), interleukin-2 receptor inducible T-cell kinase, lymphocyte-specific protein tyrosine kinase (Lck), and transmembrane glycoprotein receptor tyrosine kinase (c-Fms)
- 15.12 **Formulation:** Commercially available for oral administration as 200 mg tablets.
- 15.13 **Preparation and storage:** Refer to package insert for complete dispensing instructions. Store tablets at room temperature between 20°C and 25°C (68°F and 77°F); excursions permitted between 15°C and 30°C (59°F and 86°F).
- 15.14 **Administration:** Refer to the treatment section for specific administration instructions. The manufacturer recommends pazopanib be administered on an empty stomach, 1 hour before or 2 hours after a meal. Do not crush tablet (rate of absorption may be increased; may affect systemic exposure).
- 15.15 **Pharmacokinetic information:**
Absorption and Bioavailability: Pazopanib is absorbed orally with median time to achieve peak concentration of 2 to 4 hours after the dose. Median absolute bioavailability is 21%. Systemic exposure to pazopanib is increased when administered with food. Administration with a high-fat or low-fat meal results in an approximately 2-fold increase in AUC and C_{max}. Pazopanib should be administered at least one hour before or 2 hours after a meal.
Plasma protein binding: 99%
Half-life elimination: 30.9 hours after administration of a single 800 mg dose
Time to peak, plasma: 2-4 hours
Excretion: Primarily via feces with renal elimination accounting for < 4% of the administered dose
Metabolism: In vitro studies demonstrate pazopanib is metabolized by CYP3A4 with a minor contribution from CYP1A2 and CYP2C8.

15.16 Potential Drug Interactions:

Cytochrome P450 Effect: Pazopanib is metabolized principally by CYP3A4 with minor contributions from CYP1A2 and CYP3A4. Therefore, inhibitors and inducers of CYP3A4 may alter the metabolism of pazopanib.

CYP3A4 Inhibitors and Inducers: Coadministration of pazopanib with strong inhibitors of CYP3A4 (e.g., ketoconazole, ritonavir, clarithromycin) increases pazopanib concentrations and should be avoided. Grapefruit juice should be avoided as it inhibits CYP3A4 activity and may also increase plasma concentrations of pazopanib. CYP3A4 inducers such as rifampin may decrease plasma pazopanib concentrations. Pazopanib should not be used if chronic use of strong CYP3A4 inducers cannot be avoided.

Transporter Inhibitors: In vitro studies suggested that pazopanib is a substrate of P-glycoprotein and breast cancer resistance protein (BCRP). Therefore, absorption and subsequent elimination of pazopanib may be influenced by products that affect P-glycoprotein and BCRP. Concomitant treatment with strong inhibitors of P-glycoprotein and BCRP should be avoided.

CYP Substrates: Results from drug-drug interaction trials conducted in cancer patients suggest that pazopanib is a weak inhibitor of CYP3A4, CYP2C8, and CYP2D6 in vivo, but had no effect on CYP1A2, CYP2C9, or CYP2C19. Concomitant use of pazopanib with agents with narrow therapeutic windows that are metabolized by CYP3A4, CYP2D6, or CYP2C8 is not recommended. Coadministration may result in inhibition of the metabolism of these products and create the potential for serious adverse events.

Concomitant use of pazopanib and simvastatin increases the incidence of ALT elevations. If a patient receiving concomitant simvastatin develops ALT elevations, follow dosing guidelines for pazopanib or consider discontinuing simvastatin. Insufficient data are available to assess the risk of concomitant administration of alternative statins and pazopanib.

Concomitant administration of pazopanib with esomeprazole, a proton pump inhibitor, decreased the exposure of pazopanib by approximately 40% (AUC and C_{max}). Concomitant use of pazopanib with drugs that raise gastric pH should be avoided. If such drugs are needed, short acting antacids should be considered in place of proton pump inhibitors and H₂ receptor antagonists. Separate antacid and pazopanib dosing by several hours to avoid a reduction in pazopanib exposure.

Pazopanib should be used with caution in patients with a history of QT interval prolongation, in patients taking antiarrhythmics or other medications that may prolong QT interval, and those with relevant pre-existing cardiac disease. Baseline and periodic monitoring of electrocardiograms and maintenance of electrolytes (e.g. calcium, magnesium, potassium) within the normal range should be performed.

15.17 Known potential toxicities:

Consult the package insert for the most current and complete information. **Important Safety Information including Boxed WARNING: Severe and fatal hepatotoxicity, manifested as increases in serum transaminases (ALT, AST) and bilirubin, has been observed in clinical trials. Monitor hepatic function and interrupt, reduce or discontinue dosing as recommended.**

Common known potential toxicities, > 10%:

Cardiovascular: Hypertension, bradycardia, peripheral edema, cardiac insufficiency

Central nervous system: Fatigue, headache, dizziness

Dermatologic: Hair discoloration, exfoliative dermatitis, alopecia, dermatological disease,

hypopigmentation, palmar-plantar erythrodysesthesia

Endocrine & metabolic: Weight loss, hyperglycemia, increased thyroid-stimulating hormone (TSH), decreased serum albumin, hypophosphatemia, hyponatremia, hypomagnesemia, hypoglycemia, hyperkalemia

Gastrointestinal: Diarrhea, nausea, decreased appetite, anorexia, vomiting, dysgeusia, increased serum lipase, gastrointestinal pain, abdominal pain, mucositis, stomatitis

Hematologic & oncologic: Leukopenia, lymphocytopenia, thrombocytopenia, neutropenia, hemorrhage

Hepatic: Increased serum AST, increased serum ALT, increased serum bilirubin, decreased serum albumin, increased serum alkaline phosphatase

Neuromuscular & skeletal: Musculoskeletal pain, myalgia, weakness

Respiratory: Dyspnea, cough

Miscellaneous: Tumor pain

Less common known potential toxicities, 1% - 10%:

Cardiovascular: Chest pain, left ventricular systolic dysfunction, venous thrombosis, ischemia, myocardial infarction, prolonged QT interval on ECG, facial edema, transient ischemic attacks

Central nervous system: Insomnia, voice disorder, chills

Dermatologic: Skin rash, skin depigmentation, xeroderma, nail disease

Endocrine & metabolic: Hypothyroidism

Gastrointestinal: Dyspepsia, anal hemorrhage, gastrointestinal fistula, gastrointestinal perforation

Hematologic & oncologic: Oral hemorrhage, rectal hemorrhage

Ophthalmic: Blurred vision

Renal: Proteinuria, hematuria

Respiratory: Epistaxis, pneumothorax, hemoptysis

Frequently not defined:

Cardiovascular: Decreased left ventricular ejection fraction, hypertensive crisis

Central nervous system: Reversible posterior leukoencephalopathy syndrome

Hematologic & oncologic: Hemolytic-uremic syndrome, neutropenic infection, thrombotic thrombocytopenic purpura

Hepatic: Hepatotoxicity, severe hepatotoxicity

Infection: Serious infection

Neuromuscular & skeletal: Arthralgia, muscle spasm

Rare, less than 1% (limited to important or life-threatening):

Cardiac disease, cerebral hemorrhage, cerebrovascular accident, congestive heart failure, interstitial pneumonitis, nephrotic syndrome, pancreatitis, retinal changes (tear), retinal detachment, torsade de pointes

15.18 **Drug procurement:** Commercial supplies. Pharmacies or clinics shall obtain supplies from normal commercial supply chain or wholesaler.

15.19 **Nursing Guidelines:**

15.191 Pazopanib should be taken without food (1 hour before or 2 hours after a meal).

Should be taken whole with water and not broken or crushed. If a dose is missed, do not take if it is less than 12 hours until the next dose.

- 15.192 There are numerous drug to drug interactions between pazopanib and other agents metabolized through the P450 system. Assess patient's concomitant medications, including OTC and herbal products. Refer to appendix for medications that should be avoided or used concomitantly with caution.
- 15.193 Hypertension is a commonly reported side effect. Monitor blood pressure closely per study guidelines. Administer antihypertensives as ordered by MD.
- 15.194 Inform patient of possible changes in hair color.
- 15.195 Gastrointestinal side effects are common (diarrhea, nausea, vomiting, loss of appetite). Treat symptomatically and assess for effectiveness.
- 15.196 Due to the similarity in nature of this agent to other VEGF inhibitors (bevacizumab, VEGF-trap, etc.) monitor for signs of bleeding, thrombosis and PE. Instruct patient to report any calf tenderness, shortness of breath, chest pain or bleeding immediately.
- 15.197 Cytopenias are common. Monitor CBC w/diff and instruct patient to report any unusual bruising or bleeding and/or signs of infection to study team.
- 15.198 Monitor LFT's. Patients who have AST/ALT levels > 3x ULN and concurrent bilirubin >2X ULN should permanently discontinue pazopanib. Patients with AST/ALT levels as above and mild hyperbilirubinemia (with suspected or known Gilbert's syndrome) should be monitored weekly while continuing pazopanib.
- 15.199a Cardiac side effects (CHF, MI, chest pain, etc). While rare can be serious and life threatening. Instruct patient to report any cardiac symptoms to study team immediately.
- 15.199b RPLS, CVA, and TIA are uncommon, but are life threatening. Instruct patient to report any neurological symptoms to the study team immediately.

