8.14 Guidelines for Management of Treatment Emergent Hepatotoxicity

Event	Dose Modification Algorithms
(A). ALT of $\leq 3.0 \times$ ULN	Continue pazopanib at current dose with full panel LFTs ^c monitored as per protocol.
(B). ALT $>3.0 \times$ ULN to $\leq 8.0 \times$ ULN without bilirubin elevation (defined as total bilirubin ⁰ $<2.0 \times$ ULN or direct bilirubin $\leq 35\%$) and without hypersensitivity symptoms (e.g., fever, rash)	
Liver Event Monitoring Criteria:
 
(1) Continue pazopanib at current dose levels.
 
(2) Monitor subject closely for clinical signs and symptoms; perform full panel LFTs^a weekly or more frequently if clinically indicated until ALT/AST is reduced to Grade 1.

(C). ALT $>8.0 \times$ ULN without bilirubin elevation (defined as total bilirubin ^b $<2.0 \times$ ULN or direct bilirubin $\leq 35\%$) and without hypersensitivity symptoms (e.g., fever, rash)	
1st occurrence – Liver Event Interruption Criteria^c:
 
(1) Interrupt pazopanib until toxicity resolves to \leqGrade 1 or baseline.
 
(2) Liver imaging and other laboratory investigations should be considered as clinically appropriate.
 
(3) Monitor subject closely for clinical signs and symptoms; perform full panel LFTs^a weekly or more frequently if clinically indicated until ALT/AST is reduced to Grade 1.
 
(4) Re-treatment may be considered if ALL following criteria are met:
 
 - ALT/AST reduced to Grade 1 - Total bilirubin $<1.5 \times$ ULN or direct bilirubin $\leq 35\%$ - No hypersensitivity signs or symptoms - Subject is benefiting from therapy. 
Recurrence – Liver Event Stopping Criteria^c:
 
Discontinue pazopanib permanently and monitor subject closely for clinical signs and symptoms; perform full panel LFTs^a weekly or more frequently if clinically indicated until ALT/AST is reduced to Grade 1.

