(D). ALT $>3.0 \times$ ULN with concomitant elevation in bilirubin ⁰ (defined as total bilirubin $\geq 2.0 \times$ ULN; with direct bilirubin $>35\%$) or with hypersensitivity symptoms (e.g., fever, rash).	
Liver Event Stopping Criteria^c:
 
(1) Discontinue pazopanib immediately.
 
(2) Perform the following assessments to identify potential co-factors:
 
 - Eosinophil count - Viral serology for hepatitis A, B, C and E, cytomegalovirus, Epstein-Barr virus (IgM antibody, heterophile antibody, or monospot testing) - Anti-nuclear antibody, anti-smooth muscle antibody, Type 1 anti-liver kidney microsomal antibodies. - Serum creatinine phosphokinase for possible muscle injury caused LFT elevation - Liver imaging - Consider toxicological blood screen for possible contributing chemical/medical entities 
(3) Monitor subject closely for clinical signs and symptoms; record the appearance or worsening of clinical symptoms of hepatitis, or hypersensitivity, such as fatigue, nausea, vomiting, right upper quadrant pain or tenderness, fever rash or eosinophilia as relevant on the AE report form. Perform full panel LFTs^a weekly or more frequently if clinically indicated until LFTs are reduced to Grade 1.

Event	Dose Modification Algorithms
For isolated total bilirubin ⁰ elevation without concurrent ALT increases (defined as ALT <3 X ULN).	
(1) Isolated hyperbilirubinemia (i.e., in the absence of elevated ALT or other signs/symptoms of liver injury) does not require dose modification. Pazopanib inhibits UGT1A1 and OATP1B1, which can cause elevation of indirect (unconjugated) bilirubin in the absence of liver injury.
 
(2) If bilirubin is >1.5 x ULN in the absence of ALT elevation, fractionation of bilirubin elevation should be performed. If bilirubin is >35% direct (conjugated), further evaluation for underlying cause of cholestasis should be performed.

- a. Full panel LFTs include: AST, ALT, alkaline phosphatase, GGT, and total bilirubin. Coagulation tests should be performed as clinically indicated.
- b. Serum bilirubin fractionation should be performed if testing is available. If testing is unavailable and a subject meets the criterion of total bilirubin >1.5 x ULN, then the event should be promptly reported as an SAE.

Abbreviations: ALT alanine aminotransferase; AST aspartate aminotransferase; LFT liver function tests;; SAE serious adverse event; ULN upper limit of normal

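### Sections 8.14 and 15.198 give opposite pazopanib instructions for ALT >3 to ≤8 × ULN with total bilirubin >2 × ULN and direct bilirubin ≤35%

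*Combined protocol and SAP*

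**What the plan says.** Section 8.14 is the hepatotoxicity algorithm within Section 8.0, the dose-modification section.

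- **Rows (B) and (C)** cover ALT rises without bilirubin elevation and without hypersensitivity symptoms. Absence of bilirubin elevation is defined by alternatives: total bilirubin below 2.0 × "ULN or direct bilirubin" at or below 35%.
- **Row (B)**, ALT above 3.0 and up to 8.0 × ULN: "1) Continue pazopanib at current dose levels", with a full liver panel "weekly or more frequently if clinically indicated until ALT/AST is reduced to Grade 1".
- **Row (C)**, ALT above 8.0 × ULN. At the first occurrence: "1) Interrupt pazopanib until toxicity resolves to" Grade 1 or lower, or baseline; then "Re-treatment may be considered if ALL following criteria are met". On recurrence: "Discontinue pazopanib permanently and monitor subject closely for clinical signs and symptoms".
- **Row (D)**, the stopping row, covers ALT above 3.0 × ULN and needs either hypersensitivity symptoms or both bilirubin conditions together: total at least 2.0 × "ULN; with direct bilirubin" above 35%.

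Section 15.198, a nursing item inside the drug information section, gives its own rule: "Patients who have AST/ALT levels > 3x ULN and concurrent bilirubin >2X ULN should permanently discontinue pazopanib". Its next sentence lets pazopanib continue, with weekly monitoring, in patients with the same transaminase levels whose hyperbilirubinemia is mild and who have known or suspected Gilbert's syndrome. Neither sentence mentions the direct fraction or refers to 8.14.

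**The concern.** The two sections define the bilirubin part of the stopping rule differently. In 8.14, a total bilirubin above 2 × ULN does not count as an elevation while the direct fraction stays at or below 35%. In 15.198, the total alone decides. One set of laboratory results can therefore call for continued dosing under one section and permanent discontinuation under the other.

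Pazopanib carries a boxed hepatotoxicity warning (Section 15.17), so the dose action for a liver signal should be unambiguous. A prescriber working from 8.14 and nursing staff working from 15.198 could reach opposite actions for the same patient. The pattern is also foreseeable. In its row on isolated bilirubin elevation, 8.14 notes that pazopanib inhibits UGT1A1 and OATP1B1 and can raise indirect bilirubin without liver injury. That is a drug effect that lowers the direct fraction.

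**Working it through.** The plan states no figure to reproduce; the check is a comparison of rules.

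**Inputs.** From 8.14: the row definitions and actions given above. From 15.198: transaminases above 3 × ULN with bilirubin above 2 × ULN means a permanent stop.

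**Worked case.** Illustrative values: ALT 5 × ULN, total bilirubin 3 × ULN, direct fraction 20%, no fever or rash, no Gilbert's syndrome.

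- Row (A) needs ALT at or below 3.0 × ULN: not met.
- Row (B) needs ALT above 3.0 and up to 8.0 × ULN (5 qualifies), and total below 2.0 × ULN *or* direct at most 35% (20% satisfies the second alternative): met. Action: continue at the current dose, liver tests at least weekly.
- Row (C) needs ALT above 8.0 × ULN: not met.
- Row (D) needs direct above 35% or hypersensitivity: not met.
- The isolated-bilirubin row needs ALT below 3 × ULN: not met.
- Section 15.198: 5 > 3 and 3 > 2: met. Action: permanent discontinuation.

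For a patient on the starting dose, the instructions are 800 mg daily versus none.

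**All combinations.** Hold total bilirubin above 2 × ULN with a known direct fraction, outside the Gilbert's exception. Three ALT states × two direct-fraction states × two hypersensitivity states = 12. Section 15.198 says stop in every one.

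| Situation | Combinations | Section 8.14 | Against 15.198 |
|---|---|---|---|
| Hypersensitivity present, any ALT state or direct fraction | 3 × 2 = 6 | Row (D): stop | Agree |
| No hypersensitivity, direct >35%, any ALT state | 3 | Row (D): stop | Agree |
| No hypersensitivity, direct ≤35%, recurrent ALT >8 × | 1 | Row (C): stop permanently | Agree |
| No hypersensitivity, direct ≤35%, first ALT >8 × | 1 | Row (C): interrupt, re-treatment permitted | Differ on permission |
| No hypersensitivity, direct ≤35%, ALT >3 to ≤8 × | 1 | Row (B): continue | Contradict |

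Agreement: 6 + 3 + 1 = 10. Difference in permission: 1. Contradiction: 1. These count rule combinations, not patients.

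**The case against.** The best defence is that 8.14 plainly governs. It sits in the dose-modification section, and its rows (B) to (D) cover every bilirubin pattern. Section 15.198 is a nursing item worded as a recommendation. Other parts of Section 15 point back to the dosing rules: 15.14 for administration, 15.16 for ALT rises on simvastatin, and the boxed warning in 15.17, which tells the reader to act as recommended. Most prescribers would probably turn to 8.14 first. In the one firm contradiction, 15.198 also errs towards stopping.

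This lowers the practical risk and indicates which section should be corrected. It does not remove the conflict. None of those references is a precedence clause, and 15.198 sets its own thresholds and a permanent action without deferring to 8.14.

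Three stronger readings are tempting, and the documents do not support them.

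- *A second contradiction at a first ALT above 8 × ULN.* Row (C) only permits re-treatment. A site that interrupts and never restarts complies with both sections, so the difference is one of permission. Row (C) also carries a footnote mark c whose text is absent from the copy read. Footnote marks in that copy are inconsistent, so the lack of mark c on row (B) proves little; the row (B) comparison rests on the words of the row.
- *The Gilbert's sentence tells sites to continue above 8 × ULN, where row (C) interrupts or stops.* The sentence sets no ALT ceiling, but it reads naturally as an exception to the stopping sentence before it, and mild is undefined. At most it is ambiguous against row (C).
- *The conflict affects the primary endpoint.* Section 16.11 counts leaving protocol treatment because of an adverse event as treatment failure, so a reader might infer an effect on TFF40. The documents give no frequency for the pattern, so no effect can be derived.

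**Conclusion.** The instruction is wrong as written, with minor severity. In one defined situation, 8.14 row (B) and 15.198 cannot both be obeyed: ALT above 3 and up to 8 × ULN, total bilirubin above 2 × ULN, direct fraction at most 35%, no hypersensitivity symptoms, outside the mild Gilbert's exception. The first-occurrence case above 8 × ULN is a lesser mismatch that the same edit would remove.

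The conclusion assumes that the direct fraction has been measured, that the alternatives in row (B) are read as written, and that no precedence clause lies in the redacted text. How many patients would fall in this situation is unknown, and because mild is undefined, the Gilbert's exception may absorb some of them.

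**What to change.** Replace the thresholds in 15.198, in both the discontinuation sentence and the Gilbert's sentence, with a pointer such as: *Monitor LFTs; dose action per Section 8.14.* Each laboratory result then has one dose action.

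This rewords one item. It needs no new tests, no schedule change and no change in sample size. If the sponsor intends the stricter rule instead, rows (B) and (C) of 8.14 should be tightened to match 15.198; that would be a clinical rule change for the sponsor to decide.
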